3. TRIAL OBJECTIVES AND OUTCOMES

3.1 Objectives

3.1.1 Primary objective

- The primary objectives of the study are to: -To assess and compare the immune response measured as binding antibodies (IgG ELISA) following standard versus fractional doses of Pfizer or Moderna vaccine given as a single additional dose to adults 18 years or older in Australia who have been primed through previous vaccination with Pfizer or AstraZeneca vaccines. (Timepoint – 28 days post vaccination)
- To assess the rate and severity of reactogenicity within one-week post-booster for each schedule evaluated.

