6.1 Concealment mechanism

Randomisation will be stratified according to age (<50 and ≥50 years) and primary vaccine (*Comirnaty*[®] or *Vaxzevria*[®]). Using REDCap the participants will be randomised to one of four groups in a 1:1:1:1 allocation ratio. (see table below).

Study staff involved in administering the vaccine will use REDCap to receive the information on the participant's randomisation number and vaccine allocation so they will be aware of which vaccine the participant is receiving. The participants themselves will remain blinded to their vaccine allocation (until day 28 post vaccination). Study staff involved in assessing reactogenicity will be blinded to each participant's vaccine allocation until 28 days post vaccination, as this variable will be hidden in REDCap for blinded study staff. Study staff involved in assessing immunogenicity outcomes will remain blinded during the analysis of specimens.

Vaccines will be prepared out of sight of the participant and the blind will be maintained by applying masking tape over the vaccine syringe, so the study participant can't see the volume.

The four booster vaccines will be prepared daily by the RCH immunisation clinic and delivered to the vaccination room and stored in the vaccine fridge. Only the study staff responsible for randomisation and drawing up and checking the vaccine will be aware of which vaccine is given to each study participant.

Primary vaccine	Age	Booster vaccine	Dose given
Pfizer-BioNTech	Below 50	Pfizer-BioNTech	30µg
		Pfizer-BioNTech	15µg
		Moderna	50µg
		Moderna	20 µg
	Above 50	Pfizer-BioNTech	30µg
		Pfizer-BioNTech	15µg
		Moderna	50µg
		Moderna	20 µg
AstraZeneca	Below 50	Pfizer-BioNTech	30µg
		Pfizer-BioNTech	15µg
		Moderna	50µg
		Moderna	20 µg
	Above 50	Pfizer-BioNTech	30µg
		Pfizer-BioNTech	15µg
		Moderna	50µg
		Moderna	20 µg

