11 STATISTICAL METHODS

11.1 Sample Size Estimation

Sample size calculations were performed using nQuery 8 software. Precision-based sample size calculations were performed based on the reactogenicity outcomes. Assuming the percentage of participants reporting local or systemic reactions is 50%, 100 participants will produce a confidence interval that is 9.8 percentage points from the observed percentage. For immunogenicity, sample size calculations were based on the comparison of seroresponse rates between the standard and fractional dose groups within the non-inferiority framework. Assuming a -10% non-inferiority margin and a seroresponse rate of 95% in both groups, the study will have 90% power for the non-inferiority comparisons using 100 participants per group. If we make the more conservative assumption that the seroresponse rate is lower in the fractional-dose group (93% versus 95% seroresponse), then 100 per group will provide 66% power.

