11.3 Methods of analysis

Reactogenicity following immunisations will be presented as the number and percentage of participants self-reporting local reactions (pain; tenderness, redness; swelling at or near the injection site) and systemic reactions (fever, nausea/vomiting, headache, fatigue/malaise, myalgia), and the severity of

these reactions (mild, moderate, severe, life-threatening or fatal). Reactogenicity data will be presented separately by group and time point.

For immunogenicity, antibody levels will be presented as geometric mean titres (GMT) with 95% confidence intervals. Changes from baseline will be expressed as geometric mean fold ratios (GMFR), calculated as the ratio of the post-booster GMT to the baseline GMT. Seroresponse will be defined as a ≥ 4 -fold rise in post-booster antibody levels compared to baseline (or ≥ 2 -fold rise if the baseline (pre-booster) antibody level was ≥ 200 BAU/ml). To assess the non-inferiority of the fractional dose compared with the standard dose, comparisons will be based on the difference in percentage of participants with seroresponse. Using a non-inferiority margin of -10% (fractional-dose minus standard dose), non-inferiority will be declared if the lower limit of the 95% confidence interval around the difference in percentages is greater than -10%, where confidence intervals are calculated using Score-based methods (14)

Analyses will be performed using Stata software (15). Detailed methodology will be outlined in a separate Statistical Analysis Plan.

Primary outcome (All samples at all timepoints)

The binding IgG data using the Euroimmun S1 IgG ELISA kits will be reported as relative units/ml (RU/ml) as per manufacturer's instructions. A result of < 8 RU/ml: negative (IgG Antibodies for SARS-CoV-2 are not detected), ≥ 8 to < 11 RU/ml: borderline (IgG antibodies is indeterminate/equivocal with this sample), ≥ 11 RU/ml: positive (IgG antibodies for SARS-CoV-2 are detected). Conversion to binding antibody units (BAU/ml) will also be done using the WHO reference serum from NIBSC, UK. Data will be presented as geometric mean titres and 95% confidence intervals.

Analysis comparing fractional and standard dose groups will be based on seroresponse rate (SRR) at 28 days post study vaccine, defined as:

- ≥ 4 -fold rise in GMCs at 28 days post study vaccine from baseline among subjects with no pre-dose (< 200 BAU/ml) detectable titres

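### Section 11 plans fractional-versus-standard comparisons of 100 v 100 with no use of the randomisation strata; age-stratified intervals and a secondary per-product estimate over both primes would add information from data already collected

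*Combined protocol and SAP*

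**What the plan says.** - **Sizing.** Section 11.1 starts from "Assuming a -10% non-inferiority margin and a seroresponse rate of 95% in both groups" and concludes that "the study will have 90% power for the non-inferiority comparisons using 100 participants per group". Its more cautious case is that "the seroresponse rate is lower in the fractional-dose group (93% versus 95% seroresponse), then 100 per group will provide 66% power".
- **Design.** The synopsis and section 4.1 list eight groups: two primes, two booster products and two dose levels, with 100 people in each. A comparison of 100 v 100 is therefore, by implication, one product within one prime, and there are four of them. The text does not use the word four.
- **Randomisation.** Section 6.1: "Randomisation will be stratified according to age (<50 and ≥50 years) and primary vaccine". Section 6 also recruits to a fixed number in each stratum.
- **Analysis.** Section 11.3: "comparisons will be based on the difference in percentage of participants with seroresponse". The decision rule is that "non-inferiority will be declared if the lower limit of the 95% confidence interval around the difference in percentages is greater than -10" percentage points, using score-based intervals. The cited method paper concerns the difference between two independent proportions. Section 11 names no stratification, no age term and no estimate that combines the two primes for a product. Further detail is left to a separate SAP, which is not among the supplied documents.
- **Objective.** Section 3.1.1 compares standard with fractional Pfizer or Moderna boosters in adults "who have been primed through previous vaccination with Pfizer or AstraZeneca vaccines".

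**The concern.** Dose level is randomised in the same way within each of four prime-by-age strata, so two analyses are open that section 11 does not mention. One is to respect the age strata within each prime-specific comparison. The other is to estimate, for each product, the average dose effect over both primes from 200 v 200.

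The second matters more. In the plan's own conservative case each contrast has 66% power. Suppose the true difference is -2 points everywhere and the four contrasts are independent. The chance of a mixed set of results, some non-inferior and some not shown, is then 1 - 0.664^4 - 0.336^4 = 1 - 0.194 - 0.013 = 79%. Readers, including the funder, WHO and the national authorities named in section 16, could take that pattern for a real difference between primes or products. A pre-specified average per product, with an estimate of how the dose effect differs by prime, would help them judge it.

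**Working it through.** **Inputs.** Margin 10 points; rates 95% v 95% and 93% v 95%; 100 per group (all section 11.1). One-sided 0.025, from the lower limit of a two-sided 95% interval (section 11.3). Allocation 1:1 between fractional and standard within each product and prime (section 6). No dropout rate is given, so zero is used first.

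**Step 1. Reproduce the plan.** Normal approximation for a difference in proportions:

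Power = Φ( (0.10 - (pS - pF)) / SE - 1.96 ), with SE = √[ (pS(1 - pS) + pF(1 - pF)) / n ].

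- 95% v 95%, n = 100: SE = √(0.0950/100) = 0.0308; 0.10/0.0308 = 3.244; Φ(1.284) = 90.05%. Stated: 90%.
- 93% v 95%, n = 100: SE = √((0.0475 + 0.0651)/100) = 0.0336; 0.08/0.0336 = 2.384; Φ(0.424) = 66.4%. Stated: 66%.

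Both match. A continuity correction (83.2%, 55.0%) or one-sided 0.05 (94.5%, 77.0%) does not.

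**Step 2. One product over both primes, n = 200 per arm, same formula.**

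- 95% v 95%: SE = 0.0218; Φ(4.588 - 1.960) = 99.6%.
- 93% v 95%: SE = 0.0237; Φ(3.372 - 1.960) = 92.1%.

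**Step 3. The same comparisons with score-type intervals, as section 11.3 plans.** Exact binomial enumeration, Newcombe and Miettinen-Nurminen:

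| True rates | 100 v 100, one prime | 200 v 200, both primes |
|---|---|---|
| 93% v 95% | 58.0% | 88.3-88.7% |
| 95% v 95% | 83.2% | 98.9% |

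A stratified score test over four strata of 50 v 50, simulated 200,000 times, gives 88.3% and 98.9%. Its one-sided error is 2.3% when the truth is 85% v 95% in every stratum.

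**Step 4. Where the gain comes from.** It comes from doubling n by averaging over primes. Stratifying by age within a prime adds little. With a mean rate of 95% and an assumed 6-point gap between age groups (98% and 92%), the ratio of standard errors is √[ ((0.98×0.02 + 0.92×0.08)/2) / (0.95×0.05) ] = √(0.0466/0.0475) = 0.990. With an assumed 8-point gap (99% and 91%) it is √(0.0459/0.0475) = 0.983. That is a 1-2% gain.

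**Step 5. What averaging can hide.** Let one prime be 95% v 95% and the other 85% v 95%.

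- The averaged difference is -5 points. Its SE is ½√[ (3×0.0475 + 0.1275)/100 ] = 0.0260, so the chance of declaring non-inferiority is about Φ(0.05/0.0260 - 1.96) = Φ(-0.035) = 49%. Simulation gives 50% with a Wald interval and 45% with a Newcombe interval.
- The dose-by-prime difference is 10 points with SE 0.0520, so a test at p<0.05 detects it with about the same probability, 49% (simulated 49-50%; 62% at p<0.10).
- In 29% of simulated trials the average declares non-inferiority and no heterogeneity is flagged at p<0.05.

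**Step 6. Sensitivity, normal formula.**

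- Assumed 5% or 10% loss, conservative case: 64.2% or 61.9% for one prime (95 or 90 per group); 90.8% or 89.2% for the average (190 or 180 per arm).
- Assumed lower rates, 88% v 90%: 44% for one prime, 73% for the average.

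**The case against.** The strongest reply is that the prime-specific comparison is the question the design asks. The eight groups are built that way, section 3.1.1 assesses reactogenicity for each schedule, and a secondary objective in section 3.1.2 concerns the priming capacities of the two primary vaccines. Pooling the Pfizer booster over primes mixes a homologous with a heterologous schedule. This stands, and it is why the four comparisons should remain the primary claims. The wording of the objective does not settle the matter: it joins the two products with the same *or* that joins the two primes.

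Three further replies also stand:

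- The averaged estimate has a real cost (step 5), and the heterogeneity test is a weak guard against it.
- Retaining four contrasts means mixed results can still occur. The addition helps in reading them but does not prevent them.
- The separate SAP may already specify a stratified or per-product analysis. That the contrasts number four and are unstratified is inferred from the group sizes and from what section 11 leaves out.

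A reader might infer more than the documents support:

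- *That stratifying raises power from 66% to 92% for the same question.* It does not: the two figures belong to different questions.
- *That the trial has only a 19% chance of success (0.66^4).* No section requires all four contrasts to succeed.
- *That the age strata oblige the plan to test non-inferiority by age.* The documents use age for balance and representation, and no objective promises an age-specific conclusion.

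**Conclusion.** The point holds as an inexpensive improvement to the analysis. Nothing in section 11.1 is miscalculated: 90% and 66% both follow from the normal approximation, and the plan openly discloses the lower figure.

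As written, section 11 makes no use of the randomisation strata and gives no per-product estimate. A secondary estimate over both primes would have about 88-89% power at 93% v 95% with a score-type interval, against 58% for one prime-specific contrast (92% against 66% on the normal formula). The power of the prime-specific contrasts stays where it is. The gain assumes standard-dose seroresponse near 95% and little missing day-28 data. It is bought by averaging over primes, so the result cannot stand as a co-equal non-inferiority claim.

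**What to change.** In section 11.3, and in the SAP, before day-28 results are seen by group:

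1. Name the four prime-specific fractional-minus-standard comparisons as the primary claims, each with a score interval stratified by age. This follows the randomisation; the precision gain is small.
2. Add one pre-specified secondary estimate for each booster product: the fractional-minus-standard difference over both primes (200 v 200), with a stratified Miettinen-Nurminen 95% interval over the four prime-by-age strata.
3. Always report it beside the two prime-specific results and a dose-by-prime estimate with its confidence interval, not only a p-value.
4. State that it cannot override a prime-specific comparison that fails to show non-inferiority, and name the masking risk.
5. Do not combine the two products: their fractions differ (15/30 and 20/50).

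If the separate SAP already contains this, a cross-reference in section 11.3 closes the point. Otherwise the cost is a paragraph of text and a few lines of code, with no new participants, samples or assays.

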11.2 Population to be analysed

Analysis of this trial is planned on both the intention-to-treat population (ITT), with all participants to be analysed in the group they were randomised to, as well as on the per-protocol (PP) population, consisting of participants who adhered to the study protocol. However, it is expected that withdrawn participants may not have data to contribute at all time points as blood samples may not be collected after the time of their withdrawal.

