	
 To assess the rate and severity of reactogenicity within one-week post-booster for each group (Timepoint – 7 days post vaccination) 
Secondary objectives - (timepoint –12 months)
 
 To compare the duration of immunity, both humoral and cellular, over 12 months for fractional vs standard booster doses of the vaccines listed. To evaluate the different priming capacities of Pfizer and AstraZeneca vaccines. To evaluate the safety of the booster dose regimens.
OUTCOMES AND OUTCOME MEASURES	
Outcomes:
 
 Reactogenicity will be measured using the accepted standardised method for evaluation of systemic and local side effects following vaccination using a structured questionnaire for seven days post-vaccination. All moderate or severe reactions will be reviewed by study staff. All solicited adverse events (AE) will be collected for 7 days, all unsolicited AE will be collected for 28 days, and all medically attended AE will be collected for 3 months. SAE will be collected throughout the follow up period of 12 months. Adverse events of special interest will be categorised as per CEPI guidelines (1) Antibodies (binding and functional) and cellular immune responses will be measured (see outcome measures for details) 
Reactogenicity
 
 Reactogenicity will be measured by recording the following parameters: 
 Local reaction - pain, tenderness, erythema/redness, induration/swelling Systemic – Nausea/vomiting, headache, fatigue/malaise/myalgia, arthralgia 
Immunology endpoints
 
Binding antibody – These will be evaluated using the commercial Euroimmun S1 IgG ELISA on serum collected at 4 timepoints (baseline, 28 days, 6 months, and 12 months). For all subjects, the 28 days post-vaccination sample will be assayed within four weeks of collection.
 
Functional antibody – All samples will be assayed using the GenScript cPass SARS-CoV-2 Neutralization Antibody detection kit for both WT and Delta variant RBD antigen.
 
Neutralizing antibody - A fraction of samples (20%) will be assessed using a SARS-CoV-2 assay undertaken at the PDI, Melbourne. Testing will be at 4 timepoints for Wuhan strain and 2 Variants of Concern.

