3.2 Outcomes

3.2.1 Primary outcomes

Immune response

Binding antibody – These will be evaluated using the commercial Euroimmun S1 IgG ELISA on all serum samples collected at 4 timepoints (baseline, 28 days, 6 months, and 12 months). Assays for all subjects will be completed within 4 weeks of sample collection. For subjects who receive a fractional dose, assays on the 28 days post-vaccination sample will be performed within two weeks of collection and reviewed by the DSMB.

Reactogenicity

Reactogenicity will be measured using the accepted standardised method to evaluate systemic and local side effects following vaccination using a structured questionnaire for days post-vaccination as outlined in Table 1 below.

Table 1. Grading system for evaluation of systemic and local side effects following vaccination (11).

Local Reaction to Injectable Product				
	Mild (Grade 1)	Moderate (Grade 2)	Severe (Grade 3)	Potentially Life Threatening (Grade 4)
Pain	Does not interfere with activity	Repeated use of nonnarcotic pain reliever >24 hours or interferes with activity	Any use of narcotic pain reliever or prevents daily activity	ER visit or hospitalization
Tenderness	Mild discomfort to touch	Discomfort with movement	Significant discomfort at rest	ER visit or hospitalization
Erythema/redness ^a	2.5 – 5 cm	5.1 – 10 cm	>10 cm	Necrosis or exfoliative dermatitis
Induration/swelling ^b	2.5 – 5 cm and does not interfere with activity	5.1 – 10 cm or interferes with activity	>10 cm or prevents daily activity	Necrosis

^a The measurement should be recorded as a continuous variable in addition to grading the measured local reaction at the greatest single diameter.
 
^b Induration/swelling should be evaluated and graded using the functional scale as well as the actual measurement.
				
Systemic (General)				
	Mild (Grade 1)	Moderate (Grade 2)	Severe (Grade 3)	Potentially Life Threatening (Grade 4)
Fever (°C) Oral or axillary temperature	38.0 – 38.4	38.5 – 38.9	39.0 – 40	>40
Nausea/vomiting	No interference with activity or 1 – 2 episodes /24 hours	Some interference with activity or >2 episodes/24 hours	Prevents daily activity, or requires outpatient IV hydration	ER visit or hospitalization for hypotensive shock
Headache	No interference with activity	Repeated use of nonnarcotic pain reliever >24 hours or some	Significant; any use of narcotic pain reliever or prevents daily activity	ER visit or hospitalization

		interference with activity		

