3.2.2 Secondary outcomes

Immunogenicity

Functional antibody – All samples at all timepoints will be assayed using the GenScript cPass SARS-CoV-2 Neutralization Antibody detection kit for both WT and Delta variant RBD antigen.

Neutralizing antibody - A fraction of samples (20%) will be assessed using a SARS-CoV-2 microneutralisation assay undertaken at the PDI, Melbourne. Assays will be done at all four timepoints to the WT (vaccine) strain and for 2 Variants of concern.

Cellular immunity - Cellular immunity will be assessed on a subset of 40% of participants, with samples collected at three timepoints: baseline, 28 days, and 12-months post-vaccination as follows:

- *QuantIFERON Human IFN- γ SARS-CoV-2* (Qiagen) will be performed using heparinised whole blood
- Peripheral blood mononuclear cells (PBMCs) will also be isolated by density gradient centrifugation within 12 hours of collection and stored in liquid nitrogen at MCRI. Assays performed will include IFN- γ Elispot, intracellular cytokine assays (flow cytometry) and multiplex cytokine assays.

Safety

- All solicited adverse events (AE) will be collected for 7 days, all unsolicited AE will be collected for 28 days, and all medically attended AE will be collected for 3 months. SAE will be collected throughout the follow up period of 12 months

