10.1.3 Safety Monitoring

Monitoring will be performed according to Good Clinical Practice (GCP) guidelines by external monitors. Following written SOPs, the monitors will verify that the clinical trial is conducted, and data are generated, documented and reported in compliance with the protocol, GCP and the applicable regulatory requirements. The investigator will provide direct access to all trial related source data/documents and reports for the purpose of monitoring.

Independent Safety Monitor

An Independent Safety Monitor will be responsible for providing independent safety monitoring in a timely fashion. The Independent Safety Monitor will operate within agreed terms of reference and will provide input to the trial investigators.

Independent Data Safety Monitoring Board (DSMB)

Safety oversight will be under the direction of a DSMB. The DSMB will meet at least 6 monthly to review SAEs or AEs deemed possibly, probably or definitively related to study interventions. The DSMB will make recommendations concerning the conduct, continuation or modification of the study for safety reasons. The DSMB will meet virtually prior to the commencement of the trial then again on at least 2 occasions to review the one-month immunogenicity data for the standard and fractional-dose recipients, and to review the 6 months data. The DSMB will decide whether a fourth dose is required, based on up-to-date safety data, for participants who received a fractional dose and did not mount an adequate antibody response. The DSMB will operate under the rules of an approved charter that will be written and reviewed at the organisational meeting of the DSMB. The DSMB will be chaired by an experienced vaccine trial specialist and will contain one statistician, one adult physician and representatives from Indonesia and Mongolia. Members of the DSMB will be independent of trial conduct.

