11.4 Interim Analyses

We will conduct an interim analysis of the antibody responses after one month to ensure that the responses in the fractional dose groups are adequate. This will be assessed on both individual and group levels by the DSMB. If fractional dose responses are considered inadequate an appropriate rescue strategy will be developed, probably involving a single dose of the vaccine in question at 3 months. If the fractional dose is considered inadequate this information will be made public and shared specifically with WHO and other groups working in the field. In addition, an analysis will be undertaken once all data are collected for the 6 months analysis to review the potential need for policy changes. All such analyses will be undertaken by the trial statistician, [name].

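### If weak fractional-dose responders are offered a further dose, analysing them as randomised tilts the secondary 6- and 12-month durability comparison toward the fractional arm

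*Combined protocol and SAP*

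**What the plan says.** **Analysis sets.** Section 11.2 plans an ITT analysis "with all participants to be analysed in the group they were randomised to" and a per-protocol analysis of those who adhered to the protocol. Its only caveat is that withdrawn participants may lack later samples.

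**The further dose.** Section 11.4 plans a review of one-month antibody responses: "This will be assessed on both individual and group levels by the DSMB". If fractional-dose responses are inadequate, a rescue strategy follows, "probably involving a single dose of the vaccine in question at 3 months". Section 10.1.3 has the DSMB decide on a fourth dose "for participants who received a fractional dose and did not mount an adequate antibody response". The DSMB also meets "and to review the 6 months data". The Protocol Synopsis is looser: the DSMB reviews everyone who misses the seroresponse definition and decides whether participants are offered another booster.

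**The comparison affected.** A secondary objective in the Synopsis is "To compare the duration of immunity, both humoral and cellular, over 12 months for fractional vs standard booster doses of the vaccines listed"; Section 3.1.2 has a similar one. Section 3.2.1 assays binding antibody at baseline, day 28, 6 months and 12 months. Section 3.2.2 measures cellular immunity in a 40% subset, "with samples collected at three timepoints: baseline, 28 days, and 12-months post-vaccination as follows".

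**Where detail sits.** Section 11.3 leaves detailed methods to a separate SAP, which was not supplied.

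**The concern.** A dose at 3 months comes before both late samples. A dose offered after the 6-month review comes before the 12-month sample only. Under ITT these samples stay in the fractional arm, so the analysis describes a fractional dose with rescue if needed. The stated objective concerns the fractional booster itself.

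Sections 10.1.3 and 11.4 direct the offer at fractional-dose recipients only. At the planned 95% seroresponse rate, about 5 of 100 participants in each standard arm would also fail to respond and, on that reading, would not be re-dosed. The error therefore has a known direction, in favour of the fractional dose.

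The per-protocol set is not a clear safeguard. A dose that the protocol itself provides for need not count as non-adherence. If re-dosed participants were removed, the weakest responders would leave the fractional arm only, which also favours it.

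At stake is how well the fractional dose appears to last. Section 11.4 intends the 6-month analysis to inform possible policy changes.

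**Working it through.** **Planning figures.** Section 11.1 uses 100 per group, a margin of -10 points, and seroresponse of 95% versus 95% or 93% versus 95%. With power = Φ((0.10 − difference)/SE − 1.96) and an unpooled SE:
- 95% vs 95%: SE = √(2 × 0.95 × 0.05/100) = 0.0308; power 90.1% (stated 90%).
- 93% vs 95%: SE = √(0.95 × 0.05/100 + 0.93 × 0.07/100) = 0.0336; power 66.4% (stated 66%).

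Both reproduce. These rates give the expected number of non-responders.

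**How many could be re-dosed.** 5 to 7% of 100 is 5 to 7 per fractional arm, or 20 to 28 of the 400 fractional-dose recipients.

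**Size of the tilt.** If a share p of the fractional arm is re-dosed and each late titre is multiplied by k, the fractional/standard GMT ratio is multiplied by k^p. The documents give no k; 3 to 10 is assumed.

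| Share re-dosed | k = 3 | k = 10 |
|---|---|---|
| 5% | 1.056 | 1.122 |
| 7% | 1.080 | 1.175 |
| 2.5% (half of 5%) | 1.028 | |
| 3.5% (half of 7%) | | 1.084 |

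**Against the precision.** With an assumed log10 SD of 0.4:
- 100 per arm: half-width 1.96 × 0.4 × √(2/100) = 0.111 log10, a factor of 1.29. The tilt is 0.05 × 0.477/0.111 = 0.22 to 0.07 × 1/0.111 = 0.63 half-widths.
- 40 per arm (cellular subset, 12 months): half-width 0.175 log10, a factor of 1.50. The same tilt is 0.14 to 0.40 half-widths.

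**Waning.** If the lift has fallen to 1.5- to 3-fold by 12 months (assumed), the factor is 1.5^0.05 = 1.02 to 3^0.07 = 1.08, or 0.08 to 0.30 half-widths at 100 per arm.

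**Whole arm rescued.** With p = 1 the factor is k itself. At k = 3 that is 0.477/0.111 = 4.3 half-widths.

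**Does censoring work?** A simulation of 4,000 trials used 100 per arm, a true ratio of 1, log10 SD 0.4, a baseline/day-28 correlation of 0.3, a day-28/month-6 correlation of 0.7, and 7% non-response under the fold-rise rule of Section 11.3. With all non-responders re-dosed, the estimated ratio was:
- all-data ITT: 1.08 (k = 3) and 1.18 (k = 10);
- dropping re-dosed participants: 1.07 to 1.08;
- censoring, with baseline and day 28 kept in the model: 1.00.

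When re-dosing depended half on a factor outside the model, censoring gave 1.02 to 1.05, dropping participants 1.06 to 1.09, and ITT 1.17 to 1.18 (k = 10). The SE of the log10 ratio was 0.0565 with no re-dosing and 0.0570 with censoring, about 1% larger. The SD and correlations are assumptions, as is where baseline titres sit relative to the 200 BAU/ml cut, so these results show direction and order of size only.

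**The case against.** The strongest reply has five parts.

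- **The SAP may settle it.** This stands. A reader might infer that the trial has no rule; the documents show only that the protocol is silent.
- **The offer may not be one-sided.** The Synopsis does not limit it to fractional-dose recipients. Sections 10.1.3 and 11.4 do, so one-sidedness is the likelier reading but is not certain. If standard-dose recipients were also re-dosed, the tilt would shrink, but late samples would still not reflect the booster alone.
- **No planned test is affected.** The only comparison with a margin is day-28 seroresponse, which precedes any rescue. A reader might infer that the non-inferiority conclusion is compromised; it is not. For the late visits Section 11.3 describes GMTs with confidence intervals and sets no margin or formal ratio test. The ratio used here is one natural way to express the durability objective.
- **The ordinary case is small.** This stands. The upper figure needs every non-responder to accept a dose and an undiminished 10-fold lift in people who responded poorly to the previous booster. Partial uptake or waning reduces it.
- **Whole-arm rescue would be public.** Section 11.4 says that inadequacy of the fractional dose would be made public and shared with WHO, so late results are less likely to mislead. They would still need correct labelling.

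ITT is also a legitimate answer to a strategy question. It should be kept and named as such, but it does not answer the stated objective.

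**Conclusion.** The point holds, conditionally on a rescue dose being offered and accepted. Following Section 11.2 as written would then bias the secondary 6- and 12-month durability comparison toward the fractional dose, and the per-protocol set does not clearly correct this. With 5 to 7% re-dosed, the inflation is at most about 1.06 to 1.17, or 0.2 to 0.6 of a half-width. This rests on an assumed 3- to 10-fold lift and log10 SD of 0.4. It becomes large only if a whole arm is rescued, which the group-level review in Section 11.4 makes possible.

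Censoring reduces the bias. A reader might infer that it always removes it, but that requires re-dosing to depend on values in the model. Section 10.1.3 says that the fourth-dose decision will also draw on current safety data, so this is an assumption.

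This is a modest, inexpensive clarification that should be made.

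**What to change.** Before month-6 data are analysed, add a paragraph to Section 11.2 or 11.3, or to the SAP if it has no rule:

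1. For the 6- and 12-month fractional-versus-standard comparisons, censor samples taken after a DSMB-offered dose, in any arm. Estimate the contrast with a longitudinal model of log antibody that keeps baseline and day-28 values as outcomes. Do not simply exclude re-dosed participants.
2. State the assumption that re-dosing depends on values in the model.
3. Report the all-data ITT result alongside, labelled *fractional dose with rescue if offered*.
4. If a whole fractional arm is rescued, report its later samples descriptively.

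Optional additions are an explicit record and handling rule for COVID-19 vaccine doses received outside the trial, and a sensitivity analysis that lowers the predicted values of censored participants.

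**Cost.** One paragraph, with no change to sample size, visits or blood draws. If all non-responders are re-dosed at 3 months, about 5 to 7 samples per fractional arm leave the censored analysis at each visit (10 to 14 over both), with a standard error about 1% larger. If the SAP already has such a rule, no change is needed.
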